4.3 Exclusion Criteria

Subjects will be excluded from the study if any of the following exclusion criteria apply prior to randomization:

1. Use of Mipomersen or Lomitapide therapy within 5 months of screening
2. Treatment (within 90 days of screening) with monoclonal antibodies directed towards PCSK9
3. New York Heart Association (NYHA) class IV heart failure or last known left ventricular ejection fraction <25%
4. Major adverse cardiovascular event within 3 months prior to randomization
5. Planned cardiac surgery or revascularization
6. Uncontrolled severe hypertension: systolic blood pressure >180 mmHg or diastolic blood pressure >110 mmHg prior to randomization despite anti-hypertensive therapy
7. Active liver disease defined as any known current infectious, neoplastic, or metabolic pathology of the liver or unexplained alanine aminotransferase (ALT), aspartate aminotransferase (AST), elevation >3x ULN, or total bilirubin >2x upper limit of normal (ULN) at screening confirmed by a repeat measurement at least 1 week apart
8. Severe concomitant noncardiovascular disease that carries the risk of reducing life expectancy to less than the duration of the trial
9. History of malignancy that required surgery (excluding local and wide-local excision), radiation therapy and/or commencement of systemic therapy as treatment during the 3 years prior to randomization
10. Females who are pregnant or nursing, or who are of childbearing potential and unwilling to use at least one acceptable effective method of contraception (eg, oral contraceptives, barrier methods, approved contraceptive implant, long- term injectable contraception, intrauterine device) for the entire duration of the study.
Exemptions from this criterion:
 - a. Women >2 years postmenopausal (defined as 1 year or longer since their last menstrual period) AND more than 55 years of age
 - b. Postmenopausal women (as defined above) and less than 55 years of age with a negative pregnancy test within 24 hours of enrolment
 - c. Women who are surgically sterilized at least 3 months prior to enrolment

11. Known history of alcohol and/or drug abuse within 5 years

12. Any condition that according to the investigator could interfere with the conduct of the study, such as but not limited to:

- a. Subjects who are unable to communicate or to cooperate with the investigator.
- b. Unable to understand the protocol requirements, instructions and study-related restrictions, the nature, scope, and possible consequences of the study (including subjects whose cooperation is doubtful due to drug abuse or alcohol dependency)

- c. Unlikely to comply with the protocol requirements, instructions, and study-related restrictions (eg, uncooperative attitude, inability to return for follow-up visits, and improbability of completing the study)
- d. Have any medical or surgical condition, which in the opinion of the investigator would put the subject at increased risk from participating in the study
- e. Persons directly involved in the conduct of the study

13. Any uncontrolled or serious disease, or any medical or surgical condition, that may either interfere with participation in the clinical study, and/or put the subject at significant risk (according to investigator's [or delegate] judgment) if he/she participates in the clinical study

14. Any underlying known disease, or surgical, physical, or medical condition that, in the opinion of the Investigator (or delegate), might interfere with the interpretation of clinical study results

15. Treatment with other investigational medicinal products or devices within 30 days or 5 half-lives of the screening visit, whichever is longer

16. Previous participation in the study

17. Hypersensitivity to any of the ingredients of inclisiran

Subjects excluded for any of the above reasons may not be re-screened for participation at any time even if the exclusion characteristic has changed.

4.4 Withdrawal Criteria

All subjects have the right to withdraw from the study at any point during treatment without prejudice. The investigator can discontinue any subject at any time if medically necessary. It will be documented whether or not each subject completed the clinical study. If study treatment or observations were discontinued, the reason will be recorded and the Sponsor should be notified promptly. The reasons a subject may discontinue their participation in the study could be from one of the following:

- AE
- Death
- Subject withdrew consent
- Physician decision
- Lost to follow-up
- Initiation of protocol-prohibited lipid-lowering therapy (eg, an approved PCSK9 inhibitor)

The applicable reason above will be recorded in the eCRF. All data collected up until the time of subject withdrawal is to be entered into the eCRF. All subjects discontinuing participation in this trial should be encouraged to complete the EOS visit except for those subjects who specifically withdrew consent.

Participating study sites will be trained on the importance of completing study follow-up procedures, and collecting the documentation required for missing data values. Any withdrawn subjects will not be replaced in this study.

4.4.1 Withdrawal from Study Medication

In the event a subject withdraws or is withdrawn from the study medication (eg, receives first injection and not second injection), the investigator will inform the Medical Monitor and the Sponsor immediately. If there is a medical reason for withdrawal, the subject will remain under the supervision of the investigator for protocol-specified safety follow up procedures.

4.5 Stopping Criteria

4.5.1 Individual Subject Dosing Stopping Criteria

During the study subjects will have clinic visits at regular intervals. Dosing with study medication (inclisiran and/or matching placebo) should be temporarily discontinued or stopped in subjects with:

1. Intolerable adverse events, or if the Investigator believes that continuing dosing will be detrimental to the subject's mental or physical health. This includes severe or serious reactions at the injection site and any anaphylactic type reactions.
2. Unexplained increases in transaminases (ALT or AST) or total bilirubin as follows:
 - a. ALT or AST >8xULN
 - b. ALT or AST >5xULN for more than 2 weeks
 - c. ALT or AST >3xULN and (total bilirubin >2xULN or INR >1.5)
 - d. ALT or AST >3xULN with the appearance of fatigue, nausea, vomiting, right upper quadrant pain or tenderness, fever, rash, and/or eosinophilia (>5%)

The investigator should evaluate to see if other causes for the laboratory abnormalities are immediately apparent, such as obstructive gall bladder or bile duct disease, viral or alcoholic hepatitis, malignancy involving the liver, congestive hepatopathy, other hepatotoxins or heritable disorders.

3. Unexplained creatine kinase (CK) values >5 x ULN confirmed by repeat test when the CK elevation is associated with muscle pain, muscle tenderness and/or muscle weakness, or new onset renal dysfunction.

In the case that study medication is permanently discontinued the subject will be asked to complete the remainder of the scheduled visits without receiving study medication (inclisiran or placebo).

All trial subjects should be followed until all abnormalities return to normal or to the baseline state.

5 Treatment of Subjects

5.1 Study Medications

5.1.1 Inclisiran (also referred to as KJX839)

Investigational product (inclisiran) information is described in [Table 5-1](#).

Table 5-1 Investigational Product

Product Name:	Inclisiran for injection
Active ingredient	Inclisiran sodium
Dosage Form:	Solution for Injection
Unit Dose	Inclisiran sodium 300 mg/1.5 mL (equivalent to 284 mg inclisiran)
Route of Administration	SC use
Physical Description	Clear, colorless to pale yellow solution essentially free of particulates
Manufacturer	[REDACTED]

Investigational product preparation: The procedure for preparing investigational product is provided in the Pharmacy Manual.

Investigational product administration: Subjects will be administered a single SC injection of 300 mg Inclisiran for Injection at predefined time points as described in the Schedule of Assessments ([Table 6-1](#)). Investigational product injection will be administered by qualified clinical study site staff under the supervision of the investigator or designee. The site of injection is the abdomen, alternating sides for each injection. Do not inject into areas of active skin disease or injury such as sunburns, skin rashes, inflammation, tattoos or skin infections.

5.1.2 Placebo

For Part 1, placebo will be supplied by the Sponsor to clinical study site as sterile normal saline (0.9% sodium chloride in water for injection) for SC injection. The placebo will be blinded and look identical to the inclisiran investigational product. Placebo will be administered as a single SC injection in an amount matched to the doses within the active inclisiran arm ([Table 5-1](#)).

5.1.3 Packaging and Labeling

Investigational product (Inclisiran for Injection and matching placebo) will be provided by the sponsor in a blinded fashion. All inclisiran and placebo investigational product will look identical to each other. Medication labels will comply with regulatory requirements.

The storage conditions for each medication provided will be described on the medication label.

All inclisiran and placebo investigational product will have a yellow shroud to maintain the blind.

5.1.4 Storage

Investigational product will be stored at controlled room temperature (20°C to 25°C [68°F to 77°F], with allowable excursions between 15°C and 30°C [59°F to 86°F]) as specified in the Pharmacy Manual. Access should be strictly limited to the investigator, pharmacists, and their designees. No special procedures are required for the safe handling of Inclisiran for Injection.

5.1.5 Accountability

The investigator or designee must maintain an inventory record of investigational product (inclisiran/placebo) received and all administered to assure the regulatory authorities and the Sponsor that the new investigational product will not be dispensed to any person who is not a subject under the terms and conditions set forth in this protocol. Investigational product accountability forms and/or specific instructions can be found in the Pharmacy Manual.

The investigational product supplied for use in this study is to be prescribed only by the Principal Investigator or designated sub-investigators and may not be used for any purpose other than that outlined in this protocol.

During the study, all used investigational product containers will be kept until the monitor has reviewed the accountability records.

All unused investigational product will be destroyed on site (or returned to the packaging and labeling facility for destruction) once the investigational product has been inventoried and the monitor has reviewed the accountability records. In the event that investigational product needs to be returned for any other reason, the site will receive a written request listing the investigational product lot number(s) to be returned and the reason for the return request.

5.1.6 Product Deficiencies (Complaints) Reporting

Sites are required to report any product deficiencies (complaints) observed to the Sponsor immediately but no later than 24 hours from the time of awareness.

Product Deficiencies reporting: deficiencies related to the identity, durability, reliability, quality, safety, effectiveness or performance of a product, after it is released for distribution (European Union [EU] DIR 2001/83/EC). (Derived from Ref United States [US] 21 CFR 211.198).

Product Technical Complaint: is defined as any verbal or written expression of dissatisfaction with a Novartis product after it is released for distribution, in its identity, quality, stability, durability, usability, reliability, safety, effectiveness or performance Examples include:

- An indication that there is an unexpected physical change in the drug product such as discoloration, change in shape of the drug product, presence of particulates or any other physical change that might indicate contamination, a manufacturing defect or any other event that might indicate a compromise in product quality.
- An indication that the content does not meet its labeled volume, count, etc.
- An indication that there is an unexpected physical change in any part of the container (this includes the vial/container, any part of the seal, the cap or the label).
- An indication that the product is mislabeled.
- An indication that there is an unexpected physical change of the product or container once the product is diluted or reconstituted (the container includes the unit dose, bag, intravenous line, syringe or any other item that is in contact with the product).
- An indication that the product is falsified, tampered with, or adulterated.

5.2 Concomitant Medications

5.2.1 Prohibited Concomitant Medications

Background lipid-lowering treatment should remain stable throughout the study duration. As a result, the following medications/treatments are not permitted to be added or changed during the study:

- Additional medications prescribed to lower LDL-C after study entry (eg, statins, ezetimibe, lomitapide, mipomersen, niacin, colesevelam, bile acid absorption inhibitors)
- Monoclonal antibodies directed towards PCSK9
- Any medication taken for the purpose of lipid lowering, including over-the-counter or herbal therapies.

5.2.2 Permitted Concomitant Medications

The following medications/treatments are permitted during the study:

- Hormone replacement therapy
- Lipid-lowering medications; subjects already on a stable (≥ 30 days before screening) lipid-lowering medications (such as statins and/or ezetimibe) should remain on the dose that they have received at time of study entry
- Prescription medications prescribed to treat preexisting medical conditions such as diabetes and hypertension

- Prescription or nonprescription medications, when necessary to treat an AE, and at the discretion of the investigator

5.3 Medical Management Guidelines

5.3.1 Adverse events

Adverse events or abnormal test findings must be followed until the event (or its sequelae) or the abnormal test finding resolves, stabilizes at a level acceptable to the Sponsor/Investigator and/or returns to baseline values.

5.3.2 Pregnancy

Pregnant women are excluded from the study. If a subject becomes pregnant during the course of the study, the investigational product administration must be discontinued and the pregnancy should be followed through to outcome. Follow-up evaluation of fetus and newborn should also be performed up to 12 months after birth. Reporting of pregnancy and any associated AEs are specified in [Section 8.4.3.2](#).

5.4 Restrictions

Subjects will have to comply with the following restrictions during the study:

- Fasted for at least 8 hours for all visits for fasting lipids and glucose blood samples
- Blood donation will not be allowed at any time during the study
- Must refrain from unaccustomed strenuous physical exercise for 48 hours before the screening and any study visit until the follow-up has been completed

5.5 Blinding

5.5.1 Blinding of study medications

Part 1 of this study will be conducted under a double-blind placebo-control. Study medication will be blinded prior to distribution to the site. Each unit dose of investigational product will contain a yellow shroud to maintain the blind.

Randomization via an automated IRT will be used to assign subjects to blinded investigational product. The clinical study site pharmacist will maintain the double blind according to site-specific procedures and the Pharmacy Manual. It should be noted that inclisiran may be visually distinguishable from placebo; therefore, blinded syringes will be provided to all study sites and used to maintain the blind.

5.5.2 Method and Maintenance of Blinding

Investigational product will be blinded prior to distribution to sites. All unit doses of investigational product (inclisiran/placebo) will contain a yellow shroud to maintain the blind.

5.6 Unblinding

The unblinding of investigational product during the study can only be performed via the IRT. The Principal Investigators/designee will have authorization to unblind a subject via the IRT.

During Part 1 of the study, in the event of a suspected unexpected serious adverse reaction (SUSAR), The Medicines Company Global Pharmacovigilance (MDCO GPV) Department may be required to unblind a subject to meet reporting requirements per country specific regulations. In this case, a designated member will have authorization to unblind via the IRT.

5.6.1 In the Event of an Emergency: Unblinding a Code

In Part 1, unblinding by request of an Investigator should occur only in the event of an emergency or AE for which it is necessary to know the investigational product to determine an appropriate course of therapy for the subject. If the Investigator must identify the treatment assignment to an individual subject, an Investigator or qualified designee should request the medication information from the IRT. The documentation received from the IRT indicating the code break must be retained with the subject's source documents in a secure manner so as not to unblind the treatment assignment to other site or Sponsor personnel. The Investigator is also advised not to reveal the study treatment assignment to other site or Sponsor personnel.

6 Schedule and sequence of procedures

The Schedule of Assessments ([Table 6-1](#)) summarizes the study assessments by time point. This study consists of four periods: Screening, Randomization, Treatment, and End of Study.

- **Screening period (Days -28 to -1):** occurs prior to randomization and consists of confirming eligibility and collecting baseline assessments.
- **Randomization (Day 1):** occurs on the day of initial administration of investigational product (inclisiran or placebo).
- **Treatment period (Day 1 through Day 690):** occurs from the start of investigational product administration through the final clinic visit.
 - Dosing: Day 1 (inclisiran or placebo), Day 90 (inclisiran or placebo), Day 180 (inclisiran for placebo subjects switching to inclisiran), Day 270 (inclisiran), Day 450 (inclisiran), and Day 630 (inclisiran; final dose)
 - Additional clinic visits: Day 150, Day 180 (non-dosing visit for subjects randomized to the inclisiran arm), Day 330, Day 510, and Day 690
- **End of study (EOS) visit:** Day 720 (90 days after final dose)

The expected duration of a subject's participation in this study is approximately 734 days which includes screening, investigational product administration, and the EOS period to Day 720.

6.1 Schedule of Assessments

The schedule of assessments is provided in ([Table 6-1](#)).

If the COVID-19 pandemic limits or prevents on-site study visits, alternative methods of providing continuing care may be implemented. Phone calls or virtual contacts (e.g. teleconsult) can replace on-site study visits, for the duration of the pandemic until it is safe for the participant to visit the site again. Given the long lasting efficacy and infrequent dosing regimen of inclisiran, it is possible to introduce a more variable dosing schedule of +/- 2 months during this pandemic, which still allows subjects to receive inclisiran. If the two-month window is utilized for the next dose, the subsequent dose may be administered up to a maximum of 8 months' time from the next dose (if the next dose is given early) or within a minimum of 4 months' time (if the next dose is given late).

If a dose is not given within this two-month window, then the subject should be considered to have had a missed dose and should return as per the schedule in the protocol for the subsequent dose.

Table 6-1 Schedule of Assessments

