6.7 Additional non dosing Clinic Visits (Days 330, 510 and 690)

Subjects will return to the clinic for dosing follow-up visits on Days 330, 510, and 690. Note: for subjects randomized to the inclisiran group the Non-dosing visit on Day 180 is described in [Section 6.6](#). The following assessments will be completed during these visits:

6.7.1 Day 330

- Pregnancy test (performed locally, using central laboratory supplies, if applicable) (women of childbearing potential only)
- Weight and waist circumference
- Fasting lipid profile/biomarkers ([Section 7.2](#))
- Assessment of ADA ([Section 7.1.7.8](#))
- Central clinical laboratory (limited serum chemistry) ([Section 7.1.7](#))
- Neurological examination ([Appendix°C](#))
- Concomitant medications
- AE/SAE reporting

6.7.2 Day 510

- Fasting lipid profile/biomarkers ([Section 7.2](#))
- Central clinical laboratory (limited serum chemistry) ([Section 7.1.7](#))
- Concomitant medications
- AE/SAE reporting

6.7.3 Day 690

- Pregnancy test (performed locally, using central laboratory supplies, if applicable) (women of childbearing potential only)
- Fasting lipid profile/biomarkers ([Section 7.2](#))
- Central clinical laboratory (limited serum chemistry) ([Section 7.1.7](#))
- Concomitant medications
- AE/SAE reporting

6.8 End of Study (EOS) Visit (Day 720 - 90 days post last dose)

A subject's participation in the study is complete when the final visit, 90 days after the last dose of investigational product, has occurred. The following assessments will be completed during this visit:

- Pregnancy test (performed locally, using central laboratory supplies, if applicable) (women of childbearing potential only)
- Physical examination (including weight and waist circumference)
- Neurological examination ([Appendix°C](#))
- Vital signs: blood pressure and heart rate ([Section 7.1.3](#))
- 12-lead ECG
- Fasting lipid profile/biomarkers ([Section 7.2](#))
- Assessment of ADA ([Section 7.1.7.8](#))
- Central clinical laboratory (full serum chemistry, hematology and coagulation) ([Section 7.1.7](#))

- Urinalysis (performed locally, using central laboratory supplies)
- Concomitant medication
- AE/SAE reporting
 - All ongoing AEs or abnormal test findings will be followed until the event (or its sequelae) or the abnormal test finding resolved, stabilized at a level acceptable to the Sponsor/Investigator and/or returned to baseline values ([Section 8.4.1](#))

7 **Protocol assessments**

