10.3.3 Analysis Windows and Baseline

The observational period for the study includes the screening period (Day -28 to Day -1), the treatment period (Day 1 to Day 690), and the EOS visit (Day 720±3 weeks). Any event occurring beyond the defined observational period, even if collected on the eCRF, will not be included in the planned statistical analysis. However, all data, including that reported after the defined observational period, will be included in the subject data listings.

Unless otherwise specified, for evaluations that are collected at multiple occasions prior to initiation of investigational product administration, the latest evaluation will be considered the "Baseline" evaluation for analysis.

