10.3.4 Missing Data Handling

The sponsor will diligently follow up each subject from the beginning till end of study (Day 720±3 weeks), and make every effort to keep each subject visit within protocol specified window on all efficacy assessments of lipids/lipoproteins/biomarkers to keep missing data to the minimum

regardless of whether the subject is on study treatment, use ancillary therapies, experience an adverse event, or adhere to the protocol.

However, if a missing value indeed occurs for any efficacy parameter up to Day 180, it's going to be imputed using appropriate imputation method. The method of the imputation will be consistent with that in the other Phase III studies and the details will be in the SAP.

For all missing values after Day 180 on all efficacy parameters, for all other parameters other than efficacy, missing data will not be imputed and will be excluded from the associated analysis.

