10.4.4.1 Adverse Events

The Medical Dictionary for Regulatory Activities (MedDRA) dictionary will be used for coding AEs. An AE (classified by preferred term) occurring during the investigational product treatment period will be counted as a treatment emergent AE (TEAE) either if it is not present at baseline or if it is present at baseline but increased in severity during the treatment period.

The number (percentage) of subjects reporting TEAEs for each preferred term will be tabulated by system-organ class, by system-organ class and severity, and by system-organ class and relationship to investigational product. If more than one event occurred with the same preferred term for the same subject, the subject will be counted only once for that preferred term using the most severe or related occurrence for the summary by severity, or relationship to investigational product, respectively.

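### The pandemic dosing window can move the final visit past Day 741, but Section 10.3.3 still ends the analysed period there, so some late adverse events would be listed but not summarised

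*Protocol*

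**What the plan says.** All places are in the protocol.

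- **Dosing (Section 6.1, added by Amendment 1).** Where the pandemic limits visits, "it is possible to introduce a more variable dosing schedule of +/- 2 months during this pandemic". No dose is exempted, and a dose counts as missed only if it falls outside the two-month window.
- **Final visit (Sections 6 and 6.8).** Section 6 describes EOS as "Day 720 (90 days after final dose"). Section 6.8 says participation is complete when the final visit, "90 days after the last dose of investigational product, has occurred".
- **Collection (Sections 8.4.1 and 8.4.2).** Serious and non-serious adverse events are recorded from randomization to EOS.
- **Analysed period (Section 10.3.3).** Besides screening, it consists of "the treatment period (Day 1 to Day 690), and the EOS visit (Day 720±3 weeks"). The rule for anything later is: "Any event occurring beyond the defined observational period, even if collected on the eCRF, will not be included in the planned statistical analysis". The section adds that "all data, including that reported after the defined observational period, will be included in the subject data listings".
- **Missing data (Section 10.3.4).** It uses the same fixed end: "The sponsor will diligently follow up each subject from the beginning till end of study (Day 720±3 weeks").
- **Treatment-emergent events (Section 10.4.4.1).** An adverse event "occurring during the investigational product treatment period will be counted as a treatment emergent AE (TEAE"), subject to its status at baseline.

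**The concern.** Amendment 1 made the dose date flexible. The final visit follows the dose date, and adverse event collection follows the final visit. The analysis cutoff does not follow any of them; it stayed on the calendar. When the last injection is well behind schedule, the protocol asks sites to record events for 90 days after it and then removes the last part of that period from the planned analysis.

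What is at stake is the completeness of the open-label safety summaries. At the time of the amendment 51 subjects were still on treatment, so a few omitted events could visibly change an incidence table. Nothing is lost at the point of collection.

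**Working it through.** **Inputs**

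- Nominal final dose: Day 630 (Section 6).
- Permitted delay: 2 months (Section 6.1). I take this as 60 days and show 59 to 62.
- Final visit: last dose + 90 days (Section 6.8).
- End of the analysed period: Day 720 + 21 days (Section 10.3.3).

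**The plan's own figure**

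630 + 90 = Day 720, which reproduces the stated EOS day. The upper limit is 720 + 21 = Day 741.

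**Effect of a late final dose**

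For a delay of d days, EOS = 720 + d, and the post-dose days beyond the limit = max(0, 720 + d − 741) = max(0, d − 21).

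| Delay (days) | Dose day | EOS day | Post-dose days after Day 741 |
|---|---|---|---|
| 0 | 630 | 720 | 0 |
| 21 | 651 | 741 | 0 |
| 30 | 660 | 750 | 9 (10%) |
| 45 | 675 | 765 | 24 (27%) |
| 60 | 690 | 780 | 39 (43%) |

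At 60 days, 741 − 690 = 51 post-dose days remain inside and 780 − 741 = 39 fall outside. Taking 2 months as 59 to 62 days gives 38 to 41 days outside.

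**If the 3-week tolerance is also applied to the dose-anchored visit**

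This is my assumption; the readable text gives a tolerance only around Day 720. The visit would then fall 69 to 111 days after the dose. The threshold becomes 741 − 69 = Day 672, a delay of 42 days. At 60 days late, the earliest visit is 690 + 69 = Day 759, still 18 days beyond the limit.

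**Could it occur?**

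The amendment rationale puts the first randomization in February 2019 and the last Day 180 visit at 02-Mar-2020.

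- Earliest Day 630: 01-Feb-2019 + 629 days = 22-Oct-2020.
- Latest Day 630: taking 02-Mar-2020 as a nominal Day 180, Day 1 was 179 days earlier (05-Sep-2019), and + 629 days = 26-May-2021. Taking enrollment to 30-Sep-2019 gives 20-Jun-2021.

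Every nominal final dose therefore follows the amendment of 08-Oct-2020. Using the window still requires local approval and a pandemic restriction on visits.

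**Ceiling**

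If all 51 subjects were 60 days late, 51 × 39 = 1,989 subject-days would be excluded. Nominal Part 2 time is 51 × (720 − 180) = 27,540 subject-days, so the share is 7.2%. This is an extreme bound, not an expectation; the lower bound is zero.

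**The case against.** The strongest reply is that the final visit may not move to Day 780 at all.

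- The heading of Section 6.8 gives both Day 720 and 90 days post-dose.
- Section 6.1 lets a late dose be followed by a shorter interval, which brings subjects back to schedule.
- The amendment log, explaining a deletion from Section 4.4.1, speaks of EOS within 90 days of the last dose and points to the assessment schedule.
- The log also says that schedule was updated with the COVID-19 text, and the body of Table 6-1 is not readable here.
- Section 10.3.3 names the EOS visit as part of the period, so Day 720 could be only a nominal label.
- The SAP, not at hand, may set windows of its own.

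Part of this stands. Table 6-1 could contain a rule that resolves the matter, which limits confidence. The rest does not remove the conflict. The log remark concerns withdrawn subjects and is not operative text. The body of Section 6.8 says 90 days after the last dose. The shorter interval in Section 6.1 applies to a subsequent dose, and none follows Day 630. Sections 10.3.3 and 10.3.4 both attach a fixed window to EOS, and Section 10.3.3 states a definite exclusion instead of deferring to the SAP.

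It is also fair that Section 12.3 still lists a dose delayed by more than 30 days as a deviation, with exceptions for subject safety and withdrawal. At 30 days the loss is 9 days, or none if the visit may be three weeks early. Part 2 is open-label and descriptive, and serious event reporting, listings and review by the data monitoring committee are intact.

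**Conclusion.** The inconsistency is real and minor; confidence is medium. As written, a final dose more than 21 days late leads to adverse events after Day 741 being collected and listed but excluded from the planned Part 2 safety summaries. At 60 days late, 39 of 90 post-dose days are affected. This rests on a strict 90-day visit, on two months being about 60 days, and on Table 6-1 containing no contrary rule. How many subjects are affected is unknown and may be zero.

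A reader might infer more than the text supports:

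- **That all events after a late final dose are lost.** They are not; at 60 days late the first 51 days are still analysed.
- **That the EOS LDL-C, antibody and chemistry results are dropped.** The exclusion sentence speaks of events. Nothing readable says that a laboratory result outside the window is discarded.
- **That a Day 690 dose leaves no time for treatment-emergent events.** That holds only if Section 10.4.4.1 takes over the Day 690 end of the treatment period. The same reading would also remove Days 691 to 720 for subjects dosed on time, so it is not caused by the dosing window. It is a reason to align the wording.
- **That the efficacy conclusions are at risk.** The Day 150 primary and key secondary endpoints precede all of this.

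**What to change.** In Section 10.3.3, end the observational period at the later of Day 720 + 3 weeks and the subject's actual EOS visit, defined as 90 days after the last actual dose with the existing visit window. The later-of rule keeps Day 741 as the end when the Day 630 dose is missed or given early. Align three other places with it: the end of study in Section 10.3.4, the Day 1 to Day 690 treatment period in Section 6, and the period used for treatment-emergent events in Section 10.4.4.1.

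The cost is wording only. Section 6.8 already requires the visit and Section 8.4 already collects the events, so no visit or sample is added. The drawback is slightly unequal follow-up: a subject dosed 60 days late would be analysed to Day 780, or to 690 + 90 + 21 = Day 801 at the end of the visit window, against Day 741 for others. Late dosing already creates that inequality in collection, and the safety summaries can show follow-up time alongside the counts.
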